#### 4.8.2 Primary Efficacy Analysis

The primary efficacy analysis is based on an endpoint that is derived from the Eliciting dose (ED).

The eliciting dose, i.e. dose at which objective symptoms leading to ending the DBPCFC occurred, is documented by the investigator in the eCRF.

In the following two cases, the ED at the M12 DBPCFC is not documented in the eCRF by the investigator:

- If the M12 DBPCFC is stopped without any objective symptoms leading to ending the DBPCFC (stopping rules) or
- if the subject took the 2,000mg dose without any objective symptom leading to ending the DBPCFC.

In those cases, the last dose given at M12 DBPCFC will be considered for ED value.

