##### Partially ingested dose:

If the last dose given is only partially ingested by the subject prior to the DBPCFC stop, then the ED reported by the investigator is:

- the previous dose given if the quantity of the last dose given actually ingested by the subject is  $\leq$  to the previous dose ingested;
- the last dose given if the quantity of the last dose given actually ingested by the subject is  $>$  than the previous dose ingested.

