The above statistics will be tabulated overall and for each screening ED subgroup:

- On the ITT population (using mBOCF imputations for missing values at Month 12),

mBOCF for ED is defined as follow:

- If the DBPCFC is stopped without any of the objective symptoms leading to ending the DBPCFC (stopping rules) or if the subject took the 2,000mg dose without any objective symptom leading to ending the DBPCFC, the ED value at M12 is considered as the maximum between:

- r the last dose given at M12 DBPCFC (if the last dose given at M12 DBPCFC is only partially ingested by the subject, then the rules as defined under partially ingested dose in [section 4.8.2](#) will apply) AND
- r the ED value at screening

- For the subjects who did not undergo the M12 DBPCFC, ED value at screening is carried forward at M12.

- On the FAS and on the PP population (using observed data).

- If the M12 DBPCFC is stopped without any of the objective symptoms leading to ending the DBPCFC (stopping rules) or if the subject took the 2,000mg dose without any objective symptom leading to ending the DBPCFC, the last dose given at M12 DBPCFC will be considered for ED value. If the last dose given at M12 DBPCFC is only partially ingested by the subject, then the rules as defined under partially ingested dose in [section 4.8.2](#) will apply.

The peanut protein ED in each treatment group at Month 12 will be compared using the same ANCOVA model as described in [Section 4.8.3.3](#), but adjusted on the Baseline ED [Number 5, 11 and 13 in the pre-defined hierarchical order of the efficacy analyses].

Finally, the M12 peanut protein ED comparison will also be performed for each age group (4-5 and 6-11 years of age):

- On the overall ITT population (using MBOCF imputation),
- On the FAS,
- On the PP population.

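### SAP 4.8.2 does not settle whether the partial-dose rule applies to a Month 12 challenge that stops without symptoms, so responder status for some children depends on which reading is programmed

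*SAP*

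**What the plan says.** SAP 4.8.2 names two situations in which "the ED at the M12 DBPCFC is not documented in the eCRF by the investigator": the challenge is stopped without objective stopping symptoms, or the child takes the 2,000 mg dose without them. For both it then says "In those cases, the last dose given at M12 DBPCFC will be considered for ED value". It does not mention partial ingestion at that point.

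The next paragraph, on partially ingested doses, opens with a general condition: "If the last dose given is only partially ingested by the subject prior to the DBPCFC stop". What it defines is narrower: "then the ED reported by the investigator is" the previous dose if the amount swallowed is no more than that previous dose, and otherwise the last dose given.

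SAP 4.8.3.4 derives the ED for step 5 (ITT overall) and steps 11 and 13 (screening ED subgroups). It treats the same symptom-free stop and also starts from the last dose given, but adds "if the last dose given at M12 DBPCFC is only partially ingested by the subject, then the rules as defined under partially ingested dose" of section 4.8.2 apply. The clause appears in both the ITT text and the FAS/PP text.

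SAP 4.13 records that the Month 12 imputation methods for the primary and secondary analyses were revised for exactly these stops. It does not mention partial doses.

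**The concern.** A responder needs a Month 12 ED of at least 1,000 mg if the screening ED was above 10 mg, and at least 300 mg otherwise. If the last dose given counts in full however little was swallowed, a child can cross the threshold on part of a dose. The SAP's own rule would assign that child the step below.

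On the literal text this is what happens in step 1 and not in step 5. The same responder variable also feeds steps 2, 3, 6 and 7. Success in step 1 rests on a single criterion, a Newcombe 95% lower bound of at least 15%. A choice of derivation made after unblinding could therefore decide the result.

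**Working it through.** **1. The passages side by side, for a stop without symptoms and a partly swallowed last dose**

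| | SAP 4.8.2 (primary) | SAP 4.8.3.4 (step 5) |
|---|---|---|
| Starting value | last dose given | last dose given |
| Partial-dose clause in the same sentence or bullet | none | yes, by reference to 4.8.2 |
| Partial-dose rule as written | sets the investigator's ED, which is absent | extended to the imputed ED |

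Elsewhere the SAP treats the investigator's ED as a specific eCRF entry. Section 4.8.1.2 makes the cumulative reactive dose (CRD) missing when that entry is missing. Sections 4.8.3.6 and 4.8.3.7 use its absence to define unresponsive children.

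**2. Where the two readings part.** The Month 12 dose steps are 1, 3, 10, 30, 100, 300, 1,000 and 2,000 mg (protocol 6.1.1.2).

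| Screening ED | Last dose given | Swallowed of it | ED and status without the rule | ED and status with the rule |
|---|---|---|---|---|
| >10 mg | 1,000 mg | up to 300 mg | 1,000 mg, responder | 300 mg, non-responder |
| >10 mg | 1,000 mg | more than 300 mg | 1,000 mg, responder | 1,000 mg, responder |
| ≤10 mg | 300 mg | up to 100 mg | 300 mg, responder | 100 mg, non-responder |
| ≤10 mg | 300 mg | more than 100 mg | 300 mg, responder | 300 mg, responder |

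A partly taken 2,000 mg dose in either group, or a partly taken 1,000 mg dose when the screening ED is ≤10 mg, changes the ED but not the responder status. In the two discordant rows, step 5's maximum with the screening ED has no effect, because the screening ED is at most 300 mg and at most 10 mg respectively. Step 5 therefore uses 300 mg and 100 mg.

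**3. The plan's own power.** Inputs from SAP 4.12: 220 v 110 children, 40% v 10%, lower bound at least 15%. Summing the exact binomial probabilities of all outcomes that meet the Newcombe criterion gives 89.2%, against 90% in the SAP table.

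**4. Sensitivity at the threshold.** With Wilson limits l and u for each arm, the Newcombe lower bound is (p1 − p2) − √[(p1 − l1)² + (u2 − p2)²]. For placebo 11/110, p2 = 10.00% and u2 = 17.02%.

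- 76/220 active: p1 = 34.55%, l1 = 28.58%. 24.55 − √(5.97² + 7.02²) = 15.33%, which succeeds.
- 75/220 active: p1 = 34.09%, l1 = 28.15%. 24.09 − √(5.94² + 7.02²) = 14.89%, which fails.
- At the planned 88/220 the bound is 20.6%. Reclassifying 1, 3, 5 or 10 active responders gives 20.2%, 19.3%, 18.4% or 16.2%.

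**5. Illustration under assumed frequencies.** The documents give no frequency, so both columns on the right are assumptions.

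| True rates | Chance of success | Adding 0.5 to 2.0 points active, 0.15 to 0.6 placebo | Adding 0.5 to 2.0 points in both arms |
|---|---|---|---|
| 35% v 10% | 57.9% | 60.5% to 67.9% | 57.0% to 54.7% |
| 30% v 10% | 18.8% | 20.9% to 27.7% | 18.5% to 17.7% |

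At the planned 40% v 10%, the unequal assumption moves the chance from 89.2% to between 90.3% and 93.1%.

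**The case against.** The strongest reply is that the rule is already in the primary section. It stands immediately below the sentence at issue and before the main analysis that uses the ED. Its condition covers any stop with a partly swallowed last dose. SAP 4.8.3.4 sends children without an investigator ED to that rule, which suggests the authors thought it usable for an imputed value. On this view the reference to the investigator is loose drafting, and 4.8.3.4 needs a cross-reference only because it is a separate section. This stands as a possible reading, and it rules out calling the gap a settled omission. It does not remove the other reading, because the words assign nothing to a child whose investigator ED is absent and only 4.8.3.4 supplies the extension.

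The cases may also be few. Protocol 6.1.1.4 requires the challenge to continue to 2,000 mg or to objective stopping reactions, so a symptom-free early stop departs from procedure. The SAP nevertheless writes rules for such stops.

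A reader might infer that the wording favours active treatment, because more active children should reach the 1,000 mg step. The planned rates make that plausible, but the documents do not establish it. With equal additions in both arms the chance of success falls slightly.

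**Conclusion.** The point holds as a conflict of wording. SAP 4.8.2 and 4.8.3.4 treat the same stop differently on their literal text, two derivations can be programmed, and the primary responder status of the children in the two discordant rows is not pre-specified. The conflict is confined to stops without symptoms where at most 300 mg of a last 1,000 mg dose (screening ED >10 mg) or at most 100 mg of a last 300 mg dose (screening ED ≤10 mg) was swallowed.

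The size is unknown, because the documents give no count of such children. Around 76 v 11 responders one active child moves the lower bound by 0.44 points (15.33 − 14.89) and changes the outcome. At the planned rates the bound stays above 15% even if ten active responders are reclassified.

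Two stronger readings are not supported. One is that the SAP definitely makes a responder of any child who takes a mouthful of the 1,000 mg dose; the alternative reading prevents that. The other is that the trial is biased towards active treatment, which depends on assumed frequencies. The case for clarifying the text needs neither.

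**What to change.** Before unblinding, reconcile the two sections using the clause the SAP already contains:

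- In 4.8.2, after the sentence that assigns the last dose given, add the clause from 4.8.3.4, so that a partly swallowed last dose is handled by the partial-dose rule below.
- In that rule, replace "then the ED reported by the investigator is" with *then the ED is*, so that it covers reported and imputed values alike.

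The same partial-dose rule then applies in the primary endpoint and in step 5. The two analyses will still not use identical EDs for every child. Step 5 keeps its modified baseline-carried-forward method (the maximum with the screening ED, and carry-forward when there was no Month 12 challenge), while the primary analysis counts a missing challenge as failure. Those differences are by design.

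The cost is two wording changes. No new data should be needed, since the CRD in 4.8.1.2 and 4.8.3.3 already counts partial doses. The downside is that the responder rate may fall slightly.

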##### Partially ingested dose:

If the last dose given is only partially ingested by the subject prior to the DBPCFC stop, then the ED reported by the investigator is:

- the previous dose given if the quantity of the last dose given actually ingested by the subject is  $\leq$  to the previous dose ingested;
- the last dose given if the quantity of the last dose given actually ingested by the subject is  $>$  than the previous dose ingested.

### Main analysis

The primary efficacy endpoint is the difference between percentage of treatment responders in the active Viaskin® Peanut 250 µg group compared to the placebo group after 12 months of EPIT treatment. A subject is defined as a treatment responder if:

- The initial ED was  $\leq 10$  mg peanut protein (Screening ED subgroup 1) and the ED is  $\geq 300$  mg peanut protein at the Month 12 DBPCFC; or
- The initial ED was  $> 10$  mg peanut protein (Screening ED subgroup 2) and the ED is  $\geq 1,000$  mg peanut protein at the Month 12 DBPCFC.

The primary efficacy analysis will be performed on the ITT population, using missing=failure imputation method (which means that subjects with missing DBPCFC peanut eliciting dose value at M12 will be considered as non-responders).

The primary measure of treatment effect will be the difference in response rates between active and placebo treatment groups. The primary analysis will apply a Wald test at a 2-sided 5% significance level to evaluate a null hypothesis of no difference, and the corresponding 2-sided Newcombe 95% confidence interval (CI) for the difference in response rates will be calculated. The clinical relevance criterion for the primary analysis will be defined by a  $\geq 15\%$  lower confidence bound, and this condition will determine whether the primary objective has been successfully met.

The Wald test p-value will be calculated using the SAS® GENMOD procedure, with DIST=binomial and LINK=identity option of the MODEL statement.

The 2-sided Wilson 95% CIs of individual response rate will be presented overall and by treatment group using the SAS® FREQ procedure, with the RISKDIFF option.

All methods described above will be performed using SAS® procedures described in [Appendix 2: SAS® Code lines](#)

The study will be considered positive if the lower bound of the 95% CI of the difference between active treatment and placebo response rates is higher or equal to 15%. This 15% difference is intended to exhibit a clear robustness of the treatment effect.

### Sensitivity analyses

Several sensitivity analyses of the primary efficacy variable will be performed by running a primary efficacy analysis either on different analysis sets, or with alternative imputation methods for missing data or using other or additional covariates.

The sensitivity analyses that will be performed are the following:

Sensitivity to analysis set:

- i. On the FAS, with no imputation for missing data (subjects with missing M12 peanut challenge are excluded from the FAS)
- ii. On the PP population, with no imputation for missing data (subjects with missing M12 peanut challenge are excluded from the PP population)

Sensitivity to handling of missing data:

CCI

CONFIDENTIAL

Project Document Version No. 3.0

Project Document Effective Date: 04-Oct-2017

Page 37 of 79

- iii. On the ITT population, using multiple imputation method. Specifically, the probability distribution that imputes the missing response will rely on placebo subjects with an available response and so the missing data would mimic placebo response. Imputations will be performed using SAS® MI procedure generating 1000 sets of imputed data. Seed used for imputation will be specified (details on the implementation of multiple imputations are given in [Appendix 2.2](#)).
- iv. On the ITT population, using worst case imputation for missing data (i.e. subjects with missing M12 peanut challenge in the placebo group to be considered as responders whereas subjects in the Viaskin® group considered as non-responders)

Sensitivity to adjustment on covariates:

- v. On the ITT population, using missing=failure imputation for missing data, Cochran-Mantel-Haenszel (CMH) method with Screening ED randomization stratum (Screening ED > 10 mg/Screening ED ≤ 10 mg) as stratification variable to compute a Newcombe 95% CI for the strata-adjusted difference in response rates.
- vi. On the ITT population, using missing=failure imputation for missing data, Cochran-Mantel-Haenszel (CMH) method with region as stratification variable to compute a Newcombe 95% CI for the region-adjusted difference in response rates.
- vii. On the ITT population, using missing=failure imputation for missing data, Cochran-Mantel-Haenszel (CMH) method with age group (4-5 years of age/ 6-11 years of age) as stratification variable to compute a Newcombe 95% CI for the age group-adjusted difference in response rates.

Regarding the sensitivity analysis (iii) on the ITT population using the multiple imputation method [4] for missing data, the strategy used is described in

### Appendix 2.2: Strategy of analysis of the primary efficacy endpoint using multiple imputation of missing data.

In case of inconsistency between the primary analysis results and sensitivity analysis results, additional analyses will be performed to explore the reasons.

All data (raw and derived) related to the primary efficacy analysis and its sensitivity analyses will be tabulated in by-subject listings.

## 4.8.3 Secondary Efficacy Analyses

### 4.8.3.1 Percentage of treatment responders in each screening ED subgroup

The two first secondary efficacy analyses are the comparisons of the percentage of treatment responders in each screening ED subgroup, in the ITT population.

These analyses will be repeated as sensitivity analyses:

- i. On the FAS,
- ii. On the PP population

No imputation for missing data will be performed since subjects with missing M12 peanut challenge are excluded from these two populations.

The same analyses methods as the ones performed for the primary efficacy analysis will be used. The clinical relevance of the difference in response rates in each screening ED subgroup will be evaluated based on the lower bound of the 2-sided Newcombe 95% CI  $> 0\%$ . The p-value based on the Wald test will be presented. In the case of sparse data (at least one of the percentages is zero), no individual response rate confidence intervals and no p-value will be presented.

According to the sample size of each screening ED subgroup (if  $N < 50$ ), a Fisher's exact test will be performed instead of the Wald test, in which case exact 2-sided 95% CIs will be provided for the difference of response rate.

With respect to the hierarchical procedure described in [Table 2](#), inference of a treatment effect in ED subgroup 2 will be contingent on ruling out a  $< 15\%$  difference in response rates in the overall population (the primary analysis), and inference of ED subgroup 1 will be contingent on ruling out a  $< 0\%$  difference in response rates in ED subgroup 2.

### 4.8.3.2 Percentage of treatment responders in each age group (4-5 and 6-11 years of age)

The difference in percentage of treatment responders will also be evaluated in each age group, in the ITT subpopulations.

These analyses will be repeated:

CCI

CONFIDENTIAL

Project Document Version No. 3.0

Project Document Effective Date: 04-Oct-2017

Page 39 of 79

- i. On the FAS,
- ii. On the PP population.

The same analyses methods as the ones performed for the primary efficacy analysis will be used. The clinical relevance of the treatment effect in each age group will be evaluated based on the lower bound of the 2-sided Newcombe 95% CI  $> 0\%$ . The p-value based on the Wald test will be presented. In the case of sparse data (at least one of the percentages is zero), no individual response rate confidence intervals and no p-value will be presented.

According to the sample size of each subgroup (if  $N < 50$ ), a Fisher's exact test will be performed instead of the Wald test, in which case exact 2-sided 95% CIs will be provided for the difference of response rate.

With respect to the hierarchical procedure described in [Table 2](#), the success criterion for the comparison of treatment responders between treatments in the 6-11 years of age group (ITT) [Number 6 in the pre-defined hierarchical order of the efficacy analyses] will be claimed if the Newcombe 95% lower CI bound is  $\geq 0$  and the results for the previous efficacy comparisons in the hierarchical order met their success criteria, and the same would apply for the next comparison in the order evaluating the 4-5 years of age group (ITT) [Number 7 in the pre-defined hierarchical order of the efficacy analyses].

#### 4.8.3.3 Cumulative reactive dose of peanut protein and change from Baseline at Month 12

The following variables will be tabulated by treatment group using descriptive statistics:

- Peanut protein cumulative reactive dose (CRD) at Baseline and at M12
- Change in Peanut protein cumulative reactive dose at M12 since Baseline

The above statistics will be tabulated overall and for each screening ED subgroup:

- On the ITT population (using modified Baseline Observation Carried Forward [mBOCF] method to impute missing data at Month 12),

mBOCF for CRD is defined as follow:

- If the DBPCFC is stopped without the objective symptoms leading to ending the DBPCFC (stopping rules) or if the subject took the 2,000mg dose without any objective symptom leading to ending the DBPCFC, the CRD value at M12 is considered as the maximum between:

- r the sum of all doses given at Month 12, including also the repeated and partial doses AND
- r the CRD value at screening

- For the subjects who did not undergo the M12 DBPCFC, CRD at screening is carried forward at M12.

- On the FAS and on the PP population (using observed data)

- If the M12 DBPCFC is stopped without any objective symptoms leading to ending the DBPCFC (stopping rules) or if the subject took the 2,000mg dose without any objective symptom leading to ending the DBPCFC, the CRD at Month 12 is considered as the sum of all doses given at Month 12, including also the repeated and partial doses.

The peanut protein cumulative reactive dose in each treatment group at M12 will be compared using an analysis of covariance (ANCOVA) model. The ANCOVA model will include the treatment group, adjusted for the Baseline cumulative reactive dose value. This comparison will be performed in the overall ITT population using mBOCF imputation [Number 4 in the pre-defined hierarchical order of the efficacy analyses], as well as for each screening ED subgroup [Number 10 & 12 in the pre-defined hierarchical order of the efficacy analyses].

Additionally, this analysis will be repeated on the FAS and the PP population, using observed data, overall and for each screening ED subgroup.

Finally, the M12 peanut protein cumulative reactive dose comparison will also be performed for each age group (4-5 and 6-11 years of age):

- On the overall ITT population (using mBOCF imputation),
- On the FAS (using observed data),
- On the PP population (using observed data).

The ANCOVA will be performed through a mixed procedure. A sample of the SAS® code to be used can be found in [Appendix 2.3: Statistical analysis methods and procedures used for the analysis of the cumulative reactive dose of peanut protein at month 12.](#)

The following statistics will be presented:

- The Least square means (LS Means) by treatment group: mean for the variable obtained by the model adjusted on the covariates
- The difference between the LS Means and the associated confidence interval
- The effect size: calculated as the absolute difference in the LS means between the treatment groups divided by pooled standard deviation
- The p-value from the hypothesis test of no difference between the treatment groups based on type III sum of squares.

The treatment effect will be estimated using the difference between the treatment LS means (adjusted means). The treatment difference will be evaluated at the 5% level of significance.

The assumption of normality underlying the statistical model will be tested using the Shapiro-Wilk test. A p-value less than 0.05 will be taken to indicate evidence of non-normality. In addition, a normal probability plot of the studentized residuals will be used to investigate the normality assumption.

The assumption of homogeneity of variance of the treatment groups will be tested using Levene's test. A p-value less than 0.05 will be taken to indicate evidence of heterogeneity of variance.

If the assumptions of normality and/or homogeneity of variance underlying the statistical model are violated,  $\log_{10}$ -transformation of the data will be considered instead. In that case, the following statistics will be presented:

- The back transformed Least square means: the Geometric Least Square Means by treatment group
- The back transformed difference between the LS Means and the associated confidence interval: the geometric LS Means ratio
- The effect size
- The p-value from the hypothesis test of no difference between the treatment groups based on type III sum of squares.

If the assumptions still do not hold for  $\log_{10}$ -transformed data, in addition to the analysis of the  $\log_{10}$ -transformed data, a sensitivity analysis will be performed using an appropriate non-parametric test procedure. The treatment effect will be estimated using Hodges-Lehmann estimate of the difference in medians. The corresponding 95% confidence interval and the p-value from the hypothesis test of no difference between the treatment groups (Wilcoxon rank-sum test) will be presented. This p-value will not be adjusted for multiplicity and provided for descriptive purpose only.

#### 4.8.3.4 Eliciting dose of peanut protein and change from Baseline at Month 12

The following variables will be tabulated by treatment group using descriptive statistics:

- Peanut protein ED dose at Baseline and at M12
- Change in Peanut protein ED dose at M12 since Baseline.

The above statistics will be tabulated overall and for each screening ED subgroup:

- On the ITT population (using mBOCF imputations for missing values at Month 12),

mBOCF for ED is defined as follow:

- If the DBPCFC is stopped without any of the objective symptoms leading to ending the DBPCFC (stopping rules) or if the subject took the 2,000mg dose without any objective symptom leading to ending the DBPCFC, the ED value at M12 is considered as the maximum between:

- r the last dose given at M12 DBPCFC (if the last dose given at M12 DBPCFC is only partially ingested by the subject, then the rules as defined under partially ingested dose in [section 4.8.2](#) will apply) AND
- r the ED value at screening

- For the subjects who did not undergo the M12 DBPCFC, ED value at screening is carried forward at M12.

- On the FAS and on the PP population (using observed data).

- If the M12 DBPCFC is stopped without any of the objective symptoms leading to ending the DBPCFC (stopping rules) or if the subject took the 2,000mg dose without any objective symptom leading to ending the DBPCFC, the last dose given at M12 DBPCFC will be considered for ED value. If the last dose given at M12 DBPCFC is only partially ingested by the subject, then the rules as defined under partially ingested dose in [section 4.8.2](#) will apply.

The peanut protein ED in each treatment group at Month 12 will be compared using the same ANCOVA model as described in [Section 4.8.3.3](#), but adjusted on the Baseline ED [Number 5, 11 and 13 in the pre-defined hierarchical order of the efficacy analyses].

Finally, the M12 peanut protein ED comparison will also be performed for each age group (4-5 and 6-11 years of age):

- On the overall ITT population (using MBOCF imputation),
- On the FAS,
- On the PP population.

